4.1.1 PRIMARY OBJECTIVE

To assess the effectiveness of MONTAGE in reducing blood loss in the first week after surgery. A formula will be used to calculate blood loss during the post-surgical period up until day 7 or hospital discharge (whichever comes first). The following formula from the Harms Study Group, shown at day 3 as an example, will be used and comparisons of blood loss between the two groups will be calculated.

Proposed Solution

- $(BV \times (Hct_{\text{preop}} - Hct_{\text{day 3 postoperative}})) + (\text{ml of transfused RBC} + \text{Cellsaver}) = \text{mL of RBC lost}$

$(\text{mL of RBC} / \text{mean Hct}) \times 100 = \text{Blood Loss}$

Accounts For Both:
Intro-operative Blood Loss + Hidden Blood Loss =
Total Blood Loss

4.1.2 SAFETY OBJECTIVES

Safety objectives will include:

- Evaluation of the repaired osteotomy by measuring displacement of the edges of the bone under compression. The angular measurement is the angle between the superior endplate of the vertebral body below the PSO and the inferior endplate of the vertebral body above the PSO. Consistent with the standard of care, successful reconstruction of the osteotomy site requires observation of the residual

angle of the osteotomy and any gap that may be present. In order to demonstrate that the use of Montage does not negatively impact the desired outcome, any residual gap will be measured in millimeters and compared between the groups. This will be done by including a CT scan performed at 1-year post surgery. A 2-sided “t” test will be used for the analysis.

- To demonstrate that Montage does not interfere with the repair, evaluation of the formation of new bone, as measured by CT scans at 1-year post surgery.
- Evaluation using the VAS back pain and leg pain, Oswestry Disability Index (ODIv2.1a) and SRS-22, which will be recorded during the study and reported as outcomes scores, and compared between the two groups.
- Antifibrinolytics use and type will be recorded during the study and compared between the two groups

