The primary efficacy outcome variable for the study is the amount of post-operative bleeding compared between patients randomized 1:1 to MONTAGE or standard of care (no bone hemostat). Blood loss will be measured indirectly by formulae that provide an estimate through changes in hematocrit. A 2-sided “t” test will be used for the analysis.

Safety Endpoints:

Consistent with the standard of care, successful reconstruction of the osteotomy site requires observation of the residual angle of the osteotomy and any gap that may be present. In order to demonstrate that the use of Montage does not negatively impact the desired outcome, any residual gap will be measured in millimeters and compared between the groups. This will be done by including a CT scan performed at 1-year post surgery. A 2-sided “t” test will be used for the analysis.

NRS back pain and NRS leg pain, SRS-22 and Oswestry Disability Index (ODIv2.1a) will be compared between the two groups and also reported as secondary outcome scores. Descriptive statistics will be reported.

PROTOCOL APPROVAL

Date
.....
.....
Date
.....
[name], Ph.D
Consultant Medical Officer
ABYRX

INVESTIGATOR AGREEMENT

The signing of this protocol by the Investigator signifies that the contents have been laid down in full agreement and that the trial will be conducted according Good Clinical Practice and to the procedures described.

.....
Date
<Investigator>

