3. TRIAL SUBJECT POPULATION

3.1 NUMBER OF SUBJECTS

A multicenter study will be undertaken in the US, with up to 4-6 centers contributing 50 patients (maximum of 20 patients per center). A sample size of 25 randomly assigned patients per study group (50 subjects in total) was calculated to detect a clinically significant treatment effect of MONTAGE (90% power; alpha = 0.05, 2-sided; 10% lost-to-follow up). This calculation was performed with the assumption that subjects within the control group lose on average 1,500 mL (+/- 500mL) of blood postoperatively while subjects within the treatment group will lose 1,000 mL of blood postoperatively.

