6. STATISTICAL DESIGN

6.1 DESIGN

This is a parallel group, randomized, open, multicenter, prospective study in subjects with spinal deformities requiring a PSO procedure at a single level. Patients will be randomized 1:1 to receive either MONTAGE or no bone hemostat. Within each randomization study group, patients will be stratified according to their smoking status (non-smokers versus current smokers).

The primary objective of this study is the evaluation of post-operative blood loss in the week following surgery.

The secondary outcome will be the stability of the construct, as measured by the gap between the repaired osteotomy edges. In addition, observations will be made regarding whether the hardware repair has been maintained, and if the screws have loosened, and if the inserted rods are intact. Each repair complication will be categorized as belonging to one of the following groups: 1) hardware malplacement, 2) loosening or dislodgment, 3) nonunion or nonfusion with hardware fracture 4) nonunion or nonfusion without hardware fracture 5) peri-hardware fracture. These complications will be measured with imaging, including CT scans performed at 1-year. Fusion failure will be determined to be present if an area of perihardware lucency greater than 2 mm in thickness is present.

Malplacement of hardware will be considered present when an abnormal hardware position with hardware impingement on an important structure such as nerve or vessel is present.

Other secondary objectives will include:

- The formation of new bone at the osteotomy site, measured in mms at 1-year post surgery at the osteotomy site.
- VAS back and leg, Oswestry Disability Index (ODIv2.1a), and SRS-22 scores which will be recorded during the study and reported as outcomes scores, and compared between the two groups.
- Analysis of the MONTAGE/vertebral body interface, evaluating whether bony substitution has occurred at 1-year post-surgery. The presence or absence of bony resorption around the MONTAGE will also be reviewed.
- The use and type of antifibrinolytics will be compared between the two groups.

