6.3 ANALYSIS PLAN

The statistical analysis will be performed in conjunction with Abyrx. Analyses will be conducted on the Intention-to-Treat population (ITT), with additional Per Protocol analyses. All significance tests will be two-sided; p-values will be provided with $P(H_0) < 0.05$ indicating a significant difference.

All other analyses with respect to demographic and clinical parameters will be reported with descriptive statistics.

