6.3.2 Secondary Variables and Analyses

Several secondary analyses will be carried out; the results of any secondary analyses are exploratory.

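### The 1-year CT gap comparison is meant to demonstrate no harm from MONTAGE, but the planned two-sided t test for a difference, with no margin or confidence-interval rule, cannot show it

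*Combined protocol and SAP*

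**What the plan says.** Section 4.1.2 gives the reason for the gap comparison: "In order to demonstrate that the use of Montage does not negatively impact the desired outcome, any residual gap will be measured in millimeters". The comparison is between groups, on a CT scan at 1 year, and the method is "A 2-sided “t” test will be used for the analysis". The Summary (Safety Endpoints) says the same.

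The next bullet of 4.1.2 has a parallel aim: "To demonstrate that Montage does not interfere with the repair, evaluation of the formation of new bone". It names no method of its own. Section 6.3 has a general line giving descriptive statistics for remaining demographic and clinical parameters.

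Other sections bear on how a result would be read:

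- Section 6.1: "The secondary outcome will be the stability of the construct, as measured by the gap between the repaired osteotomy edges".
- Section 6.3.2: "the results of any secondary analyses are exploratory".
- Section 6.3 makes all tests two-sided and gives a meaning only to p < 0.05, as "indicating a significant difference".
- Section 3.1 has the only sample-size calculation ("90% power; alpha = 0.05, 2-sided; 10% lost-to-follow up"), and it is for blood loss.

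No section states a margin, a confidence-interval criterion, an expected gap, a gap SD or power for the gap. The 2 mm lucency thresholds in sections 1.4 and 6.1 define fusion failure in an individual patient. They are not margins for a difference in means.

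**The concern.** A two-sided t test asks whether the data contradict equal means. A significant result could show harm or benefit. A non-significant result shows only that equality was not ruled out, and a small trial can return that when harm is real. Showing no negative impact requires excluding a worsening of stated size, so a margin has to be fixed in advance and compared with a confidence limit. The plan has neither.

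The protocol does not say that non-significance will be read as no harm. It offers no other way to reach its stated conclusion, however, and the exploratory label in 6.3.2 conflicts with the aim of demonstrating something.

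The question matters for this product. Section 1.3 suggests that bone hemostats have stayed outside standard care probably because most are not absorbed and could hinder fusion. The support cited there for MONTAGE not interfering with healing or fusion comes from animal studies. An imprecise comparison could therefore be reported as reassurance on the main doubt about this class of product.

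**Working it through.** **1. The plan's own figure.** Section 3.1 assumes control blood loss of 1,500 mL, treatment 1,000 mL, and ±500 mL, taken here as the SD. The difference is 500/500 = 1.0 SD. By the normal formula, n per arm = 2 × (1.960 + 1.282)² / 1.0² = 21.01, so 22; 22/0.90 = 24.4, so 25. The stated 25 per arm is reproduced. It is sized for a 1.0 SD effect on blood loss and says nothing about the gap.

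**2. Inputs for the gap.** From the documents: 25 per arm, 1:1, two-sided alpha 0.05. Assumed: roughly normal gaps, equal SDs, and the 10% loss in 3.1 also holding for the 1-year CT, which leaves 22.5 per arm (about 45 in total). That 10% was set for an endpoint measured "up until day 7 or hospital discharge (whichever comes first", so losses of 0% to 30% are shown. No gap SD is given, so results are in SD units.

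**3. Precision at 10% loss.** Degrees of freedom = 43 and t = 2.0167. Half-width of the 95% confidence interval = t × √(2/n) = 2.0167 × √(2/22.5) = 2.0167 × 0.298 = 0.60 SD.

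**4. Chance of a non-significant result when MONTAGE truly worsens the gap.** With true worsening d in SD units, the test statistic is noncentral t with noncentrality d/√(2/n). At d = 0.5 and 22.5 per arm this is 0.5/0.298 = 1.68. The probability of falling between −2.0167 and 2.0167 is 0.625.

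**5. Margin that could be excluded.** If the rule were that the upper limit of the two-sided 95% interval must lie below a margin, and the true difference is zero, the last column gives the margin with 80% power.

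| Loss by 1 year | n per arm | Half-width (SD) | Non-significant at 0.5 SD | Non-significant at 0.75 SD | Margin for 80% power (SD) |
|---|---|---|---|---|---|
| 0% | 25 | 0.57 | 59% | 26% | 0.81 |
| 10% | 22.5 | 0.60 | 63% | 31% | 0.85 |
| 20% | 20 | 0.64 | 66% | 36% | 0.91 |
| 30% | 17.5 | 0.69 | 70% | 42% | 0.98 |

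At 10% loss the power to exclude a 0.5 SD margin is 37%, and a 0.75 SD margin 69%. For a larger worsening of 1.0 SD the t test does well: with 22 per arm it is non-significant only 10% of the time, and 7% with no loss.

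**6. Sensitivity to normality.** Many gaps may be zero. A simulation (22 versus 23 patients, 200,000 runs) set half the gaps to zero and made the rest lognormal with log-SD 0.7, all assumed. A mean worsening of 0.5 SD was non-significant 57% to 81% of the time, depending on how the worsening arose. This is illustrative; the conclusion does not rest on it.

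**The case against.** The strongest reply is that the plan already limits the claim. Section 6.1 makes the gap a secondary outcome and 6.3.2 makes secondary results exploratory, so the purpose clause may be loose wording that the statistical section overrides. No success criterion or decision rule depends on the gap test. A two-sided t test is a legitimate way to look for a difference in either direction, and it would usually detect a worsening of 1.0 SD.

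The safety judgement also has other support: five categories of hardware and fusion complication, CT review of screw loosening and of the interface with MONTAGE, two blinded image readers, and adverse events tabulated by arm. For new bone, the descriptive-statistics line in 6.3 arguably supplies an analysis. The SD-unit figures would apply to any t test of this size, and nobody can say from the documents whether 0.5 SD matters clinically.

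Much of this stands as to weight: the problem is one of wording and interpretation, on a secondary outcome. It does not remove the problem. The Summary and 4.1.2 class the gap under safety and keep the verb *demonstrate*. The exploratory label does not say how a null result will be read. None of the other evidence supplies a margin, and descriptive statistics cannot demonstrate non-interference for new bone.

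**Conclusion.** The concern holds and should be fixed. The plan states a no-harm conclusion for the gap and names only a test for a difference, which cannot deliver it. Even with complete follow-up, a half-SD worsening would be missed more often than not (59%; 63% at 10% loss). These sizes rest on roughly normal gaps with equal SDs and on the assumed loss by 1 year, and they cannot be translated into millimetres. The mismatch between aim and test depends on none of those assumptions. It affects how a secondary, exploratory outcome is interpreted; the primary blood-loss analysis and the sample size are untouched.

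**What to change.** In the Summary (Safety Endpoints) and section 4.1.2, replace the three sentences from the purpose clause through the t-test sentence with:

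> To assess the effect of MONTAGE on the repair, the residual gap (mm) on the 1-year CT will be summarized by group, and the mean difference (MONTAGE minus control) reported with a two-sided 95% confidence interval. This analysis is exploratory; a non-significant difference will not be interpreted as showing no negative impact.

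In the new-bone bullet of 4.1.2, delete the opening purpose clause so that the bullet begins at the evaluation itself, and report the between-group difference with a 95% confidence interval.

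This costs wording and reporting only. The interval comes from the same t procedure, with the same data, visits and patients. The downside is that the no-harm claim is given up.

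If the sponsor wants to keep that claim for the gap, the last sentence of the replacement text should give way to a margin rule. That means pre-specifying and justifying a between-group margin before any gap data by arm are seen, concluding no negative impact only if the upper 95% confidence limit is below it, and exempting the gap from the exploratory label in 6.3.2. The analysis set and the handling of missing 1-year CTs would also have to be stated. With about 45 evaluable patients this has 80% power only for a margin of about 0.85 SD or wider, so a tighter margin would probably leave the claim unproven.

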1.3 BACKGROUND INFORMATION

PEDICLE SUBTRACTION OSTEOTOMY - ASSOCIATED BLOOD LOSS

Pedicle Subtraction osteotomy (PSO) is a surgical option for treating several spinal deformities. It has been utilized in alignment disorders of the fused spine, in the lumbar spine to treat large sagittal deformities and in patients with ankylosing spondylitis with thoracolumbar kyphotic deformity (1).

PSO is a procedure most commonly performed in the lumbar and thoracic spinal regions. PSO is often avoided in the distal lumbar spine because the risk of the neurologic injury is greater and fewer fixation points are available. It has been suggested that some of the ideal candidates for PSO are those patients with a substantial sagittal imbalance > 10 to 12 cm, with a sharp angular kyphosis and patients who have circumferential fusion along multiple segments. For most patients with ankylosing spondylitis, PSO could be the treatment of choice. The procedure involves surgical excision of a wedge of bone from the posterior spine (osteotomy). The two cut edges are then drawn together by a system of screws and rods designed to apply compression and thus reduce the unnatural forward curvature of the spine.

PSO typically results in substantial loss of blood (as much as 2L) with a significant portion of the loss likely occurring at the osteotomy surfaces post-surgically. Blood loss-associated morbidities can be direct, including hypotension, organ damage (particularly cardiac, pulmonary, renal) and coagulopathy. Excessive blood loss also may require allogeneic blood transfusion, which may further result in acute lung injury, hypersensitivity reactions, infections, and immune suppression. Another concern with regard to post-operative bleeding in spinal surgery is the risk of spinal epidural hematoma formation, which might lead to spinal cord or cauda equina compression. Therefore, the control of peri-operative blood loss is considered a critical issue by spine surgeons (2,3,5).

A variety of methods have been proposed for the reduction of blood loss during or immediately after spine surgery, including preoperative use of erythropoietin, autologous blood, cell salvage, intra-operative controlled hypotension, and the use of anti-fibrinolytic drugs (6). Bone hemostats have traditionally not been part of the standard of care to promote hemostasis probably because most available options (e.g., bone wax) are nonabsorbable and thus might interfere with fusion at the osteotomy site.

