4.2.2 Randomization

The randomization will occur with the participating center contacting the central study data repository after submitting preoperative subject data; random assignment will be generated by computer. Patients will be randomized to either PSO with MONTAGE or standard of care

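### Antifibrinolytic use, which the protocol lists as a way to reduce blood loss, is only compared between arms; a planned-use covariate recorded before assignment would add precision to the primary comparison at almost no cost

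*Combined protocol and SAP*

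**What the plan says.** Section 1.3 lists methods proposed to limit blood loss during or just after spine surgery, "and the use of anti-fibrinolytic drugs" among them.

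Antifibrinolytics then appear in four places:
- as a secondary objective in section 1.4;
- as a safety objective in section 4.1.2: "Antifibrinolytics use and type will be recorded during the study and compared between the two groups";
- among the other secondary objectives in section 6.1: "The use and type of antifibrinolytics will be compared between the two groups";
- in section 4.2.3.1, which has their use recorded at the surgery visit.

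No section stratifies by antifibrinolytic use or brings it into the primary analysis. Smoking status is the only stratification factor (sections 4.1, 6.1 and 6.2). The Summary specifies a two-sided t test for the primary outcome and names no covariate. Section 6.3 leaves other clinical parameters to descriptive statistics. The exploratory multivariate calculation in section 1.4 combines measures of blood loss; it does not adjust for antifibrinolytics.

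The formula in section 4.1.1 starts from the preoperative hematocrit and is said to capture intra-operative as well as hidden loss. An antifibrinolytic effect during surgery therefore enters the primary outcome.

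Under section 4.2.2 a center obtains the assignment by "contacting the central study data repository after submitting preoperative subject data".

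**The concern.** By the protocol's own account, this variable acts on the primary outcome. It can be declared before assignment, and the protocol already intends to record it. Leaving it out of the primary comparison leaves whatever variance it explains in the error term. In a trial of 25 per arm, a visible imbalance would also leave a result that is hard to interpret, with no prespecified way to handle it.

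A separate matter is differential use. The trial is open, and section 4.2.2 and the events table in Appendix I place randomization before surgery. If so, the team may know the arm when it decides on antifibrinolytics. The Summary instead places randomization after the wedge has been cut. The timing decides whether actual use is a post-assignment variable, which could not safely be used as a covariate.

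**Working it through.** **Inputs from section 3.1.** Design parameters: "90% power; alpha = 0.05, 2-sided; 10% lost-to-follow up". Control patients are assumed to "lose on average 1,500 mL (+/- 500mL) of blood postoperatively", and "subjects within the treatment group will lose 1,000 mL of blood postoperatively". The difference is therefore 500 mL. The +/- 500 mL is read as an SD and applied to both arms. The stated size is 25 per arm.

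**Assumptions, not in the documents.** Antifibrinolytic effect d = 200-500 mL; proportion treated p = 50-80%; the 500 mL SD already includes this source of variation; planned use closely predicts actual use.

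**1. Reproduce the plan's figure.** n per arm = 2 x (1.960 + 1.282)^2 x 500^2 / 500^2 = 21.0, taken up to 22. Then 22 / 0.90 = 24.4, taken up to 25. The stated size reproduces. The exact t calculation gives 23 per arm, or 26 after dropout, so the two agree closely.

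**2. Power as planned, 22 completers per arm.** SE = 500 x sqrt(2/22) = 150.8 mL; 500 / 150.8 = 3.317; 3.317 - 1.960 = 1.357, which gives 91.3% (normal approximation; 90.0% by noncentral t).

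**3. Is chance imbalance extra error?** Take p = 50%, d = 500 mL and 25 per arm.
- SE of the difference in use = sqrt(2 x 0.25 / 25) = 0.141. The 95% range is +/- 0.277, or +/- 139 mL on the blood-loss difference.
- SE of the blood-loss difference = 500 x sqrt(2/25) = 141.4 mL. The 95% margin is +/- 277 mL.
- (139/277)^2 = 0.25, the same as the share of variance due to antifibrinolytics: 0.25 x 500^2 / 500^2 = 25%.

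The 139 mL is one component of the 277 mL margin, not an addition to it.

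**4. Gain from adjustment.** Residual SD = sqrt(500^2 - d^2 x p x (1 - p)). Power is by normal approximation with 22 per arm.

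| d (mL) | p | Residual SD (mL) | Power |
|---|---|---|---|
| none | - | 500 | 91.3% |
| 200 | 80% | 493.6 | 91.9% |
| 200 | 50% | 489.9 | 92.3% |
| 300 | 80% | 485.4 | 92.7% |
| 300 | 50% | 477.0 | 93.5% |
| 500 | 80% | 458.3 | 95.1% |
| 500 | 50% | 433.0 | 96.9% |

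At p = 95% and d = 500 mL, the variance removed is 500^2 x 0.0475 = 11,875, so the residual SD is sqrt(238,125) = 488 mL. At d = 200 mL it is sqrt(250,000 - 1,900) = 498 mL.

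**5. A single unlucky trial.** With 25 per arm, a gap in use of at least 20 points has probability 20% at p = 50% and 11% at p = 80%. A 20-point gap shifts the unadjusted difference by 0.20 x d: 40, 60 or 100 mL for d = 200, 300 or 500 mL. Given that gap, with an SD of 500 mL and noncentral t:
- if controls are the more treated arm, power falls from 93.4% to 89.0%, 86.2% or 79.1%;
- if MONTAGE has no effect, the rejection rate is 5.9%, 7.0% or 10.7%.

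These figures are conditional on the gap. Averaged over all randomizations, the type I error stays at 5%.

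**The case against.** An unadjusted t test in a randomized trial is valid, and 25 per arm reproduces without any covariate. This stands. A reader might infer that an imbalance in use biases the primary result. Step 3 shows that the chance part is already counted in the standard error, as it is for any prognostic factor left out of a randomized comparison.

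The size of the gain is unknown. The documents give neither the effect nor the rate of use, 50% use is the most favorable case, and a 500 mL effect equals the whole planned effect of MONTAGE. With 200 mL and 80% use, adjustment removes only 0.16 x 200^2 / 500^2 = 2.6% of the variance. This also stands, so the claim has to be given as a range with a low end near zero.

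A planned-use covariate cannot remove bias from differential use after the arm is known, and the protocol already compares actual use by arm. This is correct, and that comparison should stay.

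Center and surgical extent are left unadjusted too. That is true, but antifibrinolytic use is a factor that the protocol itself names as acting on blood loss and already means to record.

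Three other inferences go beyond the text:
- that the protocol regards use as an effect of MONTAGE: it says only that use is compared, and section 6.3.2 calls secondary analyses exploratory;
- that use is left to each center: the documents are silent, and the investigator discretion in section 4.2 concerns bone void fillers;
- that use is captured only at surgery: section 4.2.3.1 is the only visit that names it, but Appendix I has a medications row at every interval.

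**Conclusion.** The point holds as a cheap gain in precision, not as an error that invalidates the primary test. Under the assumptions above, the residual SD falls to about 433-494 mL and power with 22 completers per arm rises to about 92-97%. The gain shrinks if planned use predicts actual use poorly, and it nearly vanishes if almost everyone is treated. Adjustment would also make one result from a small trial less exposed to an unlucky split.

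Systematic differential use in an open trial is a possible bias that the t test's error rate does not cover. The documents give no evidence of its direction or size, and the covariate would not correct it. Whether antifibrinolytic use sits under a safety or a secondary heading changes no result.

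**What to change.** 1. Add planned antifibrinolytic (yes/no, agent) to the preoperative data that section 4.2.2 already requires before the assignment is issued. If fixed at that point, the value precedes assignment under either stated timing of randomization.
2. Prespecify planned use (yes/no) as a covariate in the primary blood-loss comparison.
3. Keep the between-arm comparison of actual use, set it against planned use, and label it a descriptive check for open-label co-intervention.
4. Reconcile the timing of randomization in the Summary with section 4.2.2 and Appendix I, and state whether actual use comes before or after assignment.

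The cost is one form field and one degree of freedom, with no extra patients or procedures and no antifibrinolytic regimen imposed. The downside is that the gain may be small if use is near universal.
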